### Planned Enrollment

	Not Hispanic or Latino		Hispanic or Latino		Total
Racial Category	Female	Male	Female	Male	
Asian	4	8	0	0	12
Black or African American	7	11	0	0	18
White	7	13	4	6	30
Total	18	32	4	6	60

7. **Subject classification:** Check off all classifications of subjects that will be specifically recruited for enrollment in the research project. Will subjects who may require additional safeguards or other considerations be enrolled in the study? If so, identify the population of subjects requiring special safeguards and provide a justification for their involvement.

 Children	 Healthy	 Fetal material, placenta, or dead fetus
 Non-English Speaking	 Prisoners	 Economically disadvantaged persons
 Decisionally Impaired	 Employees	 Pregnant women and/or fetuses
 Yale Students	 Females of childbearing potential	

NOTE: Is this research proposal designed to enroll children who are wards of the state as potential subjects?

Yes  No

8. **Inclusion/Exclusion Criteria:** What are the criteria used to determine subject inclusion or exclusion?

#### Inclusion Criteria:

Subjects with a diagnosis of idiopathic PD defined according to the UK Brain Bank diagnostic criteria (Hughes et al., 1992) and on a stable dopaminergic medication regimen will be included.

#### Exclusion Criteria:

- Age < 40 years
- Non-English speaking
- Pregnancy
- Breastfeeding
- Excessive alcohol consumption (> 7 drinks per week for women, > 14 drinks per week for men) or substance use

- History of a neurological disorder such as a brain tumor, stroke, central nervous system infection, multiple sclerosis, movement disorder (other than PD), or seizures
- History of schizophrenia, bipolar disorder, attention deficit disorder, or obsessive compulsive disorder
- History of head injury with loss of consciousness
- Metallic surgical implants or traumatically implanted metallic foreign bodies
- Inability to lie flat for about an hour
- Discomfort being in small, enclosed spaces
- Dementia (Montreal Cognitive Assessment score < 21)
- Hoehn & Yahr stage > 3 (i.e., able to stand and walk, but not fully independent)
- Focal neurological findings on exam that suggest cerebral pathology other than that associated with parkinsonism
- Motor symptoms that could potentially introduce too much motion artifact in the imaging data (e.g., MDS-UPDRS resting tremor score > 1 in limbs, head/chin tremor, or dyskinesia by history or exam).

9. How will **eligibility** be determined, and by whom? [Write here](#)

Eligibility will be determined based on age, MRI safety screening, and clinical criteria as listed in Inclusion/Exclusion Criteria. After subjects pass the MRI safety and medical history screening, [name] will determine eligibility.

10. **Risks:** Describe the reasonably foreseeable risks, including risks to subject privacy, discomforts, or inconveniences associated with subjects participating in the research.

The proposed research plan involves a neurological examination, administration of questionnaires and paper-pencil tests, behavioral testing, and MRI. Subjects who are on dopaminergic medications (e.g., carbidopa/levodopa, dopamine receptor agonists) will be asked to hold the first morning dose of medications temporarily for research visits 1 and 4. Only patients who would be safely able and willing to comply with this requirement will be enrolled. Immediately upon completion of testing, subjects will resume their routine medication schedule. If at any point of testing the subjects experience discomfort as a result of being off their medication, the testing will be terminated and they will be given their medication. Subjects will always be scanned after they take their dopaminergic medications. The potential risks associated with individual study procedures are as follows:

Clinical Evaluation:

The clinical evaluation including neurological examination, questionnaires, and paper-pencil tests does not entail any medical risk. Subjects may choose to stop participating in the surveys/questionnaires at any time.

MRI in 3 Tesla scanner:

Subjects are at risk for injury from the scanner, if they have metal objects in their bodies (e.g., pacemakers, aneurysm clips, metallic prostheses, implanted delivery pumps, cochlear implants, shrapnel fragments). Welders and metalworkers are also at risk for injury because of possible presence of small metal fragments in the eye, of which they may be unaware. Individuals with fear of confined spaces (i.e., claustrophobia) may become anxious during MRI. The scanner makes a thumping noise created by the radiofrequency waves necessary for forming the images. The noise can be loud enough to damage hearing. Lying flat in the scanner for an hour might cause discomfort for some subjects. On rare occasions, some people might feel dizzy, get an upset stomach, have a metallic taste or feel tingling sensations or muscle twitches. These sensations usually go away quickly.

11. **Minimizing Risks:** Describe the manner in which the above-mentioned risks will be minimized.

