## 2.2. Subjects:

Subjects who are interested in participating in the study will undergo medical history and MRI screening for eligibility in-person or via phone/email. The standard MRI Safety Questionnaire that was developed at the MRRC will be used. Subjects will also be asked detailed questions to determine whether they would be safely able and willing to comply with the requirement of holding the morning dose of their medication temporarily for research visits 1 and 4. Conditions that are related to being “off” medication by history such as excessive slowness and/or stiffness, freezing of gait, severe balance problems and/or falls, and severe anxiety will be deemed unsafe. Only subjects who would be safely able and willing to comply with this requirement will be enrolled.

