## 2.4. Research Visit 1:

### 2.4.1. Clinical Evaluation:

All subjects will be asked to temporarily hold the morning dose of their dopaminergic medication on Visit 1. Upon obtaining informed consent to participate in the study, [name] will perform an initial physical and neurological examination on all subjects. The diagnosis of idiopathic PD will be made according to the UK Brain Bank diagnostic criteria (Hughes et al., 1992). Cognitive and emotional problems may interfere with imagery performance. To rule out dementia and depression, the Montreal Cognitive Assessment test and Beck Depression Inventory-II will be administered, respectively (Nasreddine et al., 2005; Beck 1997). The Movement Disorders Society-Unified Parkinson’s Disease Rating Scale (MDS-UPDRS) (Goetz et al., 2008) and Hoehn & Yahr staging (Hoehn and Yahr, 1998) are standardized clinical rating scales to determine disease severity and stage in PD. Part III of the MDS-UPDRS is the objective motor examination part that also includes Hoehn & Yahr staging. This part will be videotaped for all subjects. The videos will be viewed and exam features scored by another neurologist with movement disorders training ([name]) who is blind to subjects’ group assignment. The standardized motor function tests (timed up and go, 10-m walking, 2-min endurance walking, five

times sit-to-stand, turning in place 360 degrees, and Physical Performance Test) will be administered to measure movement speed and vigor. All of these are standardized tests and scales, and are commonly used in clinical practice to assess symptom severity in PD.

Immediately after this initial assessment, subjects will take their dopaminergic medication. Subsequently, subjects will be administered additional self-evaluation questionnaires. These include: Starkstein Apathy Scale (Starkstein et al., 1992), Spielberger State-Trait Anxiety Inventory (Spielberger et al., 1982), Parkinson disease Fatigue Scale (Brown et al., 2005), Parkinson disease quality of life scale (PDQ39) (Peto et al., 1995), Self-Assessment Parkinson's Disease Disability Scale (SPDDS) (Biemans, et al., 2001) and Multidimensional Assessment of Interoceptive Awareness (MAIA) questionnaire (Mehling et al, 2012). Motor imagery skills will be tested using the Movement Imagery Questionnaire-3 (MIQ-3) (Williams et al., 2012).

After visit 1, subjects will be randomized to PD-neurofeedback and PD-control groups (see 13. Statistical Considerations).

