#### **2.7.1. Clinical Evaluation:**

The MDS-UPDRS part III motor examination and the standardized motor function tests will be repeated for all subjects. The MDS-UPDRS part III will be videotaped and the videos will be scored by a neurologist with movement disorders training ([name]), who is blind to subjects' group assignment.

Immediately after this final assessment, subjects will take their dopaminergic medication.

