**Confidentiality:**

Hard copies of all medical information collected from study participants will be kept in a locked filing cabinet. Unique identifiers will be used to label all data. Electronic files will be maintained on password-protected research computers. The imaging data will be stored on secure and HIPAA compliant servers in the MRRC. All team members will use password-protected research computers. Strict standards of confidentiality will be upheld at all times.

12. **Data and Safety Monitoring Plan:** Include an appropriate Data and Safety Monitoring Plan (DSMP) based on the investigator's risk assessment stated below. (Note: the HIC will make the final determination of the risk to subjects.)

- a. What is the investigator's assessment of the overall risk level for subjects participating in this study? **Minimal risk**
- b. If children are involved, what is the investigator's assessment of the overall risk level for the children participating in this study? *Write here*
- c. Include an appropriate Data and Safety Monitoring Plan. Examples of DSMPs are available here <http://your.yale.edu/policies-procedures/forms/420-fr-01-data-and-safety-monitoring-plans-templates> for
  - i. Minimal risk
  - ii. Greater than minimal
- d. For multi-site studies for which the Yale PI serves as the lead investigator:
  - i. How will adverse events and unanticipated problems involving risks to subjects or others be reported, reviewed and managed? *Write here*
  - ii. What provisions are in place for management of interim results? *Write here*
  - iii. What will the multi-site process be for protocol modifications? *Write here*

13. **Statistical Considerations:** Describe the statistical analyses that support the study design.

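### The risk section assigns no risk to walking, turning and chair-rise tests done with the morning dose held, and the supplied text describes no precaution specific to these tests and no recording of falls

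*Combined protocol and SAP*

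**What the plan says.** **Risk statement.** Item 10 (Risks) opens by listing the study components, among them "administration of questionnaires and paper-pencil tests, behavioral testing, and MRI". Risk entries follow under two labels only, clinical evaluation and MRI. The first reads: "The clinical evaluation including neurological examination, questionnaires, and paper-pencil tests does not entail any medical risk".

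**Content of the clinical evaluation.** Section 2.4.1, headed Clinical Evaluation, has subjects hold the morning dose at Visit 1 and take it after the assessment. Within that assessment it lists "The standardized motor function tests (timed up and go, 10-m walking, 2-min endurance walking, five" and, continuing over the page, "times sit-to-stand, turning in place 360 degrees, and Physical Performance Test) will be administered to measure movement speed and vigor". Section 2.7 holds the dose again at Visit 4, and section 2.7.1 adds: "The MDS-UPDRS part III motor examination and the standardized motor function tests will be repeated for all subjects".

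**Recognition of the hazard.** Section 2.2 asks about the subject's history off medication and says that conditions including "freezing of gait, severe balance problems and/or falls, and severe anxiety will be deemed unsafe". Only subjects judged safe and willing to hold the dose are enrolled.

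**Other safeguards.** Item 10 repeats that enrolment limit and ends testing, with medication given, if being off medication causes discomfort. Item 8 excludes Hoehn & Yahr stages above 3.

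**Monitoring.** Item 11 (Minimizing Risks) deals with consent, termination of participation, MRI, pregnancy and confidentiality. Item 12 rates the study as minimal risk. Beneath that rating stands the template instruction "Include an appropriate Data and Safety Monitoring Plan" with a link to examples, and no plan text follows.

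**The concern.** The tests that involve rising, walking and turning are the study procedures in which a fall is most readily foreseen, and they are done with the dose held. They carry no stated risk, although the protocol's own screening section shows that its authors had the hazard in mind. Once a hazard is left out of the risk statement, nothing later in the document prompts a precaution or a data field for it.

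Two things are at stake. The first is that the account of risk given for ethical review is incomplete. The second is harms reporting. Section 2.1 calls this a Phase II randomized trial, and item 1 motivates it by the need for therapies with few adverse effects. Followed as written, the supplied plan produces no comparison of harms between arms. A fall between visits could also affect the Visit 4 motor scores, and nothing in the supplied text would let the analyst see it.

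**Working it through.** The plan states no fall rate or safety figure to reproduce, and no alpha, power or effect size enters the point. The check is a comparison of the text, plus one count.

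**1. Does the no-risk sentence cover the motor tests?** There are two readings.
- If clinical evaluation in item 10 means what the heading of section 2.4.1 means, the sentence covers the timed walking, turning and chair-rise tests. It then conflicts with section 2.2, which treats balance problems and falls off medication as unsafe.
- If the sentence covers only the three activities it names, the motor tests belong to behavioral testing, which item 10 lists and then gives no risk entry.

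On either reading these tests have no stated risk. The first is a contradiction and the second an omission.

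**2. What do the existing safeguards reach?**
- *Screening (section 2.2, repeated in item 10).* It removes subjects with known off-medication problems. It rests on history and may be done by phone or email. The criterion does not appear in the exclusion list of item 8, although item 9 bases eligibility on the listed criteria.
- *Hoehn & Yahr limit (item 8).* Stage 3 may enrol. The only staging described is part of the Visit 1 motor examination, within the same dose-held assessment, so it is not described as a filter applied beforehand.
- *Stopping rule (item 10).* It is triggered by discomfort, which need not precede a fall. No record of a terminated test is described.

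**3. Is there a precaution during the tests?** Item 11 specifies continuous observation for MRI. It says nothing about how the gait, turning and chair-rise tests are supervised.

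**4. Is there a recording procedure?**
- The adverse-event wording in item 11 concerns stopping a scan.
- The note in section 2.4.1 on informing the ethics board concerns imminent risk found through the depression questionnaire.
- Section IV, item 2 says case report forms hold medical information, test scores and behavioral data, and names no adverse-event item.
- The injury route in Section VI, item 4 depends on the subject making contact.
- Item 13 contains no safety analysis.

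**5. Scale.** Inputs: 60 randomized subjects (section 2.1 and item 13), two dose-held visits (sections 2.4.1 and 2.7), and 35% drop-out between Visits 1 and 4 (item 13).
- Maximum sessions at the planned size: 60 × 2 = 120.
- With the stated drop-out: 60 + (1 − 0.35) × 60 = 60 + 39 = 99.
- With six tests per session: 120 × 6 = 720 and 99 × 6 = 594 test administrations.

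An expected number of falls would be sessions × fall rate. The documents give no rate, so the calculation stops here.

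**The case against.** The strongest reply is that the protocol does guard against this hazard. It identifies patients for whom holding the dose is unsafe and declines to enrol them, limits disease stage, and stops testing on discomfort. The disputed sentence names the examination, questionnaires and paper-pencil tests, so it can fairly be read as not speaking about walking tests at all. Section IV, item 1 mentions data and safety monitoring boards, and Section VI, item 4 tells injured subjects to contact the study doctor. Consent pages are not in the supplied text, and the link in item 12 leaves room for a monitoring plan filed separately. No planned efficacy analysis depends on the point.

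Most of this stands, and it rules out several stronger conclusions that a reader might draw:
- *That falls are not guarded against at all.* Sections 2.2, item 8 and item 10 show otherwise. What is missing is a precaution specific to the motor tests.
- *That the tested subjects are a group the protocol regards as prone to off-medication falls.* Those patients are screened out, and the subjects tested are the remainder. Residual risk is plausible, because screening is by history and stage 3 may enrol, but the documents do not state it.
- *That some number of falls would go unrecorded.* Any such count needs an outside rate.
- *That harms would differ by arm because only the neurofeedback arm physically performs movements in imagery practice.* The examples in section 2.5.1.1 are simple limb movements, at a visit where medication is taken as scheduled. The documents do not support a difference.

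The reply does not supply a risk entry for the motor tests, a description of their supervision, or a procedure for recording falls.

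**Conclusion.** The point holds in this limited form. Item 10 either contradicts section 2.2 or omits the motor tests, and in both cases dose-held walking, turning and chair-rise testing has no stated risk. General safeguards exist, but the off-medication criterion is missing from item 8. The supplied text describes no precaution specific to these tests and no recording of falls or other adverse events.

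It touches at most 120 dose-held sessions, or about 99 with the stated drop-out. These counts assume 60 randomized subjects, and the lower one assumes that all 60 complete Visit 1 testing. Item 6 gives fifty subjects, and the interim sample-size recalculation could change the total. The finding on recording is confined to the supplied text and would be answered by a separate monitoring plan that covers falls. The point concerns the risk statement and harms reporting. It does not affect the power or validity of the planned motor comparison, and it should be corrected because correction is cheap.

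**What to change.** - **Reconcile** section 2.2, section 2.4.1 and items 8, 10 and 12, so that the off-medication criterion, the content of the clinical evaluation and the stated risks agree.
- **Item 10:** replace the no-risk sentence with one that names the risk of falls in motor testing with the dose held.
- **Item 11:** have the investigators state how these tests are supervised. The choice of procedure is theirs.
- **Item 12:** insert the monitoring plan, or refer to it if it is a separate file.
- **Case report forms, identical in both arms:** at Visits 1 and 4, one field for a fall or near-fall and one for a test terminated because of off-medication symptoms. At Visits 2 to 4, one question on falls or new symptoms since the last visit.
- **Item 13:** add a table of these events by arm.

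The cost is revised wording, a few fields on existing forms and a less favourable risk statement for ethical review. No extra visits are needed.

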**Informed consent:**

Each subject will receive an oral and written explanation of the purposes, procedures, and risks of the study in language appropriate for the individual's level of understanding. The subjects will be given the opportunity to ask questions and discuss any concerns with the investigators. Subsequently, they will have to demonstrate understanding of the study procedures and what is expected of them. All members of the research team are trained to obtain informed consent. The signed consent form will be placed in the study record.

**Subject Monitoring:**

Subject's participation will be terminated under the following conditions: 1) Subject develops a serious medical condition. 2) Subject is not compliant with protocol evaluations. 3) Subject requests withdrawal from the study. During MRI, a member of the research team will always be present in the scanning room and monitor all subjects continuously. Scanning will be terminated immediately upon subject's request or if an adverse event occurs.

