**Statistical Analyses:**

Demographic and clinical data: Independent-sample t-tests will be performed to compare the baseline values between the PD-neurofeedback and PD-control groups ( $p < 0.05$ , two-tailed).

**Aim 1:** A 2x2 mixed ANOVA with an interaction term will be performed to assess group differences in right insula-dmFC functional connectivity (between-subject factor: group, within-subject factor: right insula-dmFC functional connectivity during the first and last control scan, interaction: group x insula-dmFC functional connectivity). Post-hoc tests will be Bonferroni-corrected,  $p < 0.05$ .

**Aim 2:** Within-group one-sample t-tests will be performed on the right insula and dmFC resting-state functional connectivity maps. A 2x2 mixed ANOVA with an interaction term will be performed to assess group differences in resting-state functional connectivity (between-subject factor: group, within-subject factor: resting-state functional connectivity pre- and post-intervention, interaction: group x resting-state functional connectivity). All group analyses will be corrected for multiple comparisons using the false discovery rate procedure ( $p < 0.05$ , two-tailed) (Genovese et al., 2002).

**Aim 3:** The scores (i.e., time required for completion) of the motor function tests will be z-transformed and summed to obtain a composite motor function score for each subject. A 2x2 mixed ANOVA will be performed to compare the differences in motor functioning between the groups pre- and post-training (between-subject factor: group, within-subject factors: MDS-UPDRS motor exam and composite motor function scores, interaction: group x motor assessment). Post-hoc tests will be Bonferroni-corrected,  $p < 0.05$ .

**Exploratory Aims:** A paired-sample t-test will be performed to assess the differences in the whole-brain functional connectivity associated with the imagery and video-watching tasks. The results will be corrected for multiple comparisons using the false discovery rate procedure ( $p < 0.05$ , two-tailed) (Genovese et al., 2002).

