**Power analysis:** The sample size calculation is based on the clinically important difference (CID) in the primary motor outcome measure. Approximately a 5-point decrease in the mean MDS-UPDRS motor exam score after an intervention has been defined as a moderate CID (Schrag et al., 2006; Shulman et al., 2010). In this study, we expect a moderate CID. We used the mean and standard deviation of the MDS-UPDRS motor exam scores ( $24 \pm 9$ ) of a large group of subjects with PD (N = 347) as the population mean and standard deviation (Shulman et al., 2010). Assuming  $\alpha = 0.05$  and power = 0.80, 22 subjects are required for a moderate CID. Considering the possibility of a 35% drop-out rate between Visits 1 and 4, we will plan to recruit 30 subjects each for the PD-neurofeedback and PD-control group, total of 60 subjects. We will also perform an adaptive interim statistical analysis based on the primary motor outcome (Bauer and Kohne, 1994). If the p values fall between 0.023 (efficacy boundary) and 0.5 (futility boundary), then we will recalculate the sample size based on conditional power (e.g., 0.80). If the p value is  $< 0.023$  (i.e., significant difference) or  $> 0.5$  (i.e., no hope to find a significant difference), we will terminate the study.

**Randomization:** Group assignment of subjects will be determined by the end of Visit 1. We will use a covariate adaptive randomization method (Lin et al., 2015). Age and gender are important variables and need to be controlled during randomization. This method will take into account age and gender and sequentially assign each new subject accordingly. This approach will allow us to balance the two groups in terms of age and gender.

**Potential problems:** 1) Variability in neurofeedback learning will be expected. We aim to reduce variability by providing personalized and detailed motor imagery scripts and facilitate learning with homework. 2) In general, attrition rate can be an issue especially in control groups. Our active control design will help minimize this by controlling for subject engagement in tasks during visits and at home, and for time spent with research staff.

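### The Aim 3 pre/post ANOVA uses only subjects with a Visit 4 score although up to 35% may be lost after randomisation; a baseline-adjusted analysis by assigned group would remove the baseline-related part of any resulting bias

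*Combined protocol and SAP*

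**What the plan says.** **Timing.** On randomisation, Section I, item 13 states: "Group assignment of subjects will be determined by the end of Visit 1". Loss between Visits 1 and 4 is therefore essentially post-randomisation.

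**Termination.** Item 11, Subject Monitoring, gives three grounds for ending participation: serious illness, the subject's request, and "Subject is not compliant with protocol evaluations". It does not say whether outcomes are still sought afterwards, or whether data already collected stay in the analysis.

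**Outcome.** Section 2.7.1 (Visit 4): "The MDS-UPDRS part III motor examination and the standardized motor function tests will be repeated for all subjects". This is the only post-training motor assessment.

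**Analysis.** Item 13, Aim 3: "A 2x2 mixed ANOVA will be performed to compare the differences in motor functioning between the groups pre- and post-training". No analysis population, missing-data method or sensitivity analysis is named.

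**Attrition.** The power analysis writes "Considering the possibility of a 35% drop-out rate between Visits 1 and 4" and raises recruitment to 30 per group. Under Potential problems it adds "In general, attrition rate can be an issue especially in control groups", followed by "Our active control design will help minimize this by controlling for subject engagement in tasks during visits and at home".

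**The concern.** In a 2x2 mixed ANOVA with one pre and one post value, the group-by-time test is a two-sample comparison of change scores. A subject without Visit 4 has no change score and drops out. If those who leave differ in severity from those who stay, and this selection differs between arms, the remaining groups are no longer comparable at baseline. A change score does not correct for that: when the pre-post correlation is below 1, milder subjects tend to drift up and more severe subjects down. Unequal selection on baseline then appears as a treatment effect, or hides one.

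Severity-related loss is plausible from the text. The Visit 4 motor tests are done with the morning dose held (Section 2.7), and item 10 stops testing if being off medication causes discomfort. The interim rule in item 13 is also based on the primary motor outcome, so if it uses the same contrast, a shift could affect the decision to stop or resize.

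**Working it through.** **The plan's own figures.** Item 13 gives a 5-point target, SD 9, alpha 0.05, power 0.80, 22 subjects, 35% drop-out and 30 per group.
- 22 x 1.35 = 29.7, rounded to 30, which matches. Dividing instead, 22 / 0.65 = 33.8, gives 34.
- 30 x 0.65 = 19.5 expected completers per arm, below 22.
- The 22 is matched by a one-sample one-sided t-test (21.5, rounded up). Whether that suits a two-arm comparison is a separate matter and is not needed here.

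**Assumptions (not in the documents).** The same SD of 9 at both visits; pre-post correlation r = 0.5 to 0.7; a true effect of -5; drop-out in arm k of p_k, with its odds multiplied by OR = 1.65 to 2.7 per SD of baseline severity.

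**Formula.** Let m_k be the mean standardised baseline among completers in arm k: m_k = E[z(1 - pi(z))] / (1 - p_k), where logit pi(z) = a + z ln(OR) and a is set so that pi averages p_k. Mean change among completers is (arm effect) - 9(1 - r)m_k, so

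bias of the change contrast (neurofeedback minus control) = -9(1 - r)(m_NF - m_C).

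**Numbers for 45% control and 25% neurofeedback.** m_C is about -0.21 (OR 1.65) or -0.37 (OR 2.7).
- *Gradient in controls only* (m_NF = 0). Smallest: 9 x 0.3 x 0.21 = 0.6. Largest: 9 x 0.5 x 0.37 = 1.7.
- *Same gradient in both arms* (m_NF about -0.12 or -0.21). Smallest: 9 x 0.3 x (0.21 - 0.12) = 0.24, or 0.25 before rounding m. Largest: 9 x 0.5 x (0.37 - 0.21) = 0.72.

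| Drop-out control / neurofeedback | Gradient | Size of bias, points | Share of 5 |
|---|---|---|---|
| 45% / 25% | controls only | 0.6 to 1.7 | 11 to 34% |
| 45% / 25% | same in both arms | 0.3 to 0.7 | 5 to 14% |
| 40% / 30% | same in both arms | 0.1 to 0.4 | 2 to 8% |
| 35% / 35% | same in both arms | about 0 | 0% |

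In the first three rows the contrast overstates the benefit. The sign reverses if milder controls leave instead. Simulation with 1,000,000 subjects per arm agrees with the formula. In the 45% / 25% scenarios, regressing Visit 4 on group and baseline returns -4.98 to -5.04, so baseline adjustment removes this bias.

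**Drop-out that depends on response.** Assume correlation 0.3 between response and drop-out, and SD of change 9. The selection factor phi(z_p)/(1 - p) is 0.424, 0.570 and 0.720 at p = 0.25, 0.35 and 0.45.
- 45% v 25%, selective in both arms: 0.3 x 9 x (0.720 - 0.424) = 0.8 points.
- 35% loss, selective in one arm only: 0.3 x 9 x 0.570 = 1.5 points.

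Baseline adjustment does not remove these shifts.

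**Precision.** The SD of change is 9 x sqrt(2(1 - r)) and the baseline-adjusted SD is 9 x sqrt(1 - r^2). Their ratio is sqrt((1 + r)/2): 0.866 at r = 0.5 and 0.922 at r = 0.7, so the standard error falls by 13% and 8%. At 19.5 per arm it goes from 2.88 to 2.50 (r = 0.5) and from 2.23 to 2.06 (r = 0.7).

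**The case against.** Four points weigh on the other side.

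1. A reader might infer that the protocol expects drop-out to fall mainly on controls. It does not say so. The 35% is an overall possibility without a split by arm. The remark about control groups is general, and the next sentence says that the active control should reduce the problem. Daily reminders for all subjects (Section 2.5.3.2) and matched staff time for controls (Section 2.6.2) serve the same end. The 45% v 25% split is therefore only an illustration.
2. A reader might take a completers-only analysis to be a written rule. It is not. It follows from a two-time-point ANOVA with no provision for missing values. The termination rule concerns participation and does not order data to be discarded.
3. A reader might take the termination ground to cover poor adherence to imagery practice. The text names evaluations, not training or homework. Some subjects ended on this ground will be those who do not attend Visit 4, so offering the visit will recover only part of the missing data.
4. The bias may be nil, and even 1.7 points is below the standard error of 2.2 to 2.9 points for the change contrast.

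All four stand as limits on the claim. They do not justify the planned contrast: bias does not shrink as recruitment rises, its direction cannot be known beforehand, and a method chosen after seeing who left carries little weight.

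**Conclusion.** The point holds in a limited form. The planned Aim 3 contrast relies on subjects with a Visit 4 score, after a possible post-randomisation loss that the plan meets only with extra recruitment. Under the stated assumptions the bias is about 0.3 to 0.7 of 5 points when loss is unequal and severity acts alike in both arms, up to 1.7 points when severity drives loss in controls only, and about zero when loss and selection are equal. Any claim that the motor comparison will be biased by a large part of the target effect goes beyond the documents, because the split, the severity gradient and the correlation are all assumed. The change is still worth making: baseline adjustment removes the baseline-dependent part and lowers the standard error by about 8 to 13% at correlations of 0.7 to 0.5, even if nobody is lost selectively.

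**What to change.** **Item 13, Aim 3.** Make the primary motor analysis a baseline-adjusted comparison of Visit 4 scores by assigned group (ANCOVA, or the equivalent constrained longitudinal model). Include the baseline score and the randomisation covariates age and gender, and use all randomised subjects with available data. Add one sensitivity analysis in which missing Visit 4 scores are imputed and then shifted by a prespecified delta, varied separately by arm, because baseline adjustment does not deal with loss related to response.

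**Item 11, Subject Monitoring.** State that ending participation for non-compliance with evaluations does not remove data already collected, and that the Visit 4 motor examination already planned is still offered to subjects who have not withdrawn consent. This concerns data collection only and leaves the grounds for termination as they are.

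**Cost.** A few sentences in the protocol, slightly more analysis, and some effort to follow up subjects who would otherwise be lost. Including less compliant subjects may dilute the estimate slightly.
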